2. AIMS

2.1 Primary aim

This study aims to evaluate the process of a CEC development after 16 months from its implementation.

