3. MATERIALS AND METHODS

1. Intervention set-up

Italian Context

Evaluating a Clinical Ethics Committee (CEC) implementation process in an Oncologic Research Hospital. A process evaluation study using Normalization Process Theory .

In Italy, CECs are mainly slowly growing entities, resulting from voluntary local efforts rather than regional or national impetus (Hurst 2007). The last national survey on the current role and practices of ethics consultations among Italian ethics committees in both clinical and research settings demonstrated that very few CECs are available in some Italian hospitals. . Still, they represent local, spontaneous and unregulated experiences (De Panfilis et al., 2019). 'CECs' role, functions and establishment have not been regulated by any national recommendation yet, despite an intense debate is ongoing on the development of national recommendation regarding ethics consultation (Italian Committee for Bioethics, Motion, January,30 2020; Furlan 2015; Italian Committee for Bioethics, Opinion, March,31,2017; draft law on *Disposizioni in materia di morte volontaria medicalmente assistita* , 2021).

On July, 13, 2020, the Clinical Ethics Committee (CEC) was deliberated by the General Directorate of the Health Care Company of Reggio Emilia. CEC is an ethical intervention promoted by the BU of the Local Health Authority of Reggio Emilia. The BU is an experimental research unit implemented in 2016 by the Scientific Directorate to promote quality of care for patients, familiars, and HPs through research activity on daily clinical practice's ethical issues. The BU research activities already integrated the development, implementation and evaluation of ethics interventions in clinical practice.

The evaluation study is part of a larger PhD research program related to developing, implementing, and first evaluating a CEC. The PI of the study is a Ph.D. candidate in Bioethics with a Master in Philosophy and documented expertise in qualitative research. The co-PI is a health researcher with a Ph.D. in Bioethics and established expertise in research, ethics consultation, and ethical education and training in clinical practice. The intervention is targeted to all the HPs employed by the Local Health Authority of Reggio Emilia.

Description of the intervention: the CEC

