The CEC's composition, and task were delineated with a 'top-down' approach, accordingly with data from the scientific literature (Schildmann et al., 2019) and the Recommendations of the Italian Committee for Bioethics,(Italian Committee for Bioethics, Opinion of Mar 31 2017). Composition and Regulations were also deliberated by the General Directorate on November 11, 2020.

-Composition:

The CEC is composed of 15 members representing the different professionals and figures involved in the decision-making process. Of these, 9 are internal and 6 are external to the Health Care Company to guarantee the 'CEC's independence. The stable core is composed of 8 HPs in adult and pediatrics care, 1 representative of patient associations, 2 jurists and 4 experts in bioethics. Occasionally, other members will take part in ethics consultation but only in decisions whose presence appears necessary, according to the patients' needs (e.g. religious, cultural mediators, psychologists, social workers). Due to the experimental feature of the CEC, components were selected personally by the Head of the BU due to their competencies and expertise in the field.

-Role, tasks and Procedures

Evaluating a Clinical Ethics Committee (CEC) implementation process in an Oncologic Research Hospital. A process evaluation study using Normalization Process Theory .

The Regulation states the 'CEC' nature, aims, tasks and procedures. CEC is responsible for

- a) the evaluation of clinical cases that are not part of the clinical and pharmacological experimentation by ethics consultation targeting HPs or health care team (*ethics consultation*);
- b) the proposal and conduction of institutional ethics training program, bioethical awareness of citizenship (*ethics education*) and
- d) the analysis of moral problems related to clinical practice (e.g. choice criteria in the allocation of resources, suspension of treatments, request for medically assisted suicide, minors, and consent, substitute decision-makers, ethical aspect of communication, immigration issues) and the development of policy on specific moral issues (*policy development*).

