CEC meets once a month through online meetings. Each HP employed by the Health Care Company of Reggio Emilia can ask for ethics consultation by an online request. Ethics consultation can be discussed during regular meetings by all 'CEC's members or, in a specific case, by a small sub-group, identified by the 'CEC's President on the evaluation of their particular competencies. If necessary, external experts can participate in the CEC meetings for specific advice on the 'President's specific recommendation.

CEC is also provided by a Secretariate, responsible for the back-office activities.

2. Process evaluation study using Normalization Process Theory

Implementation of CEC in a hospital setting is a complex intervention.

In order to perform a rigorous evaluation of the implementation process of the CEC of the Local Health Authority of Reggio Emilia, we applied the Normalization Process Theory (NPT) as the methodological research strategy .

Accordingly with a recent survey on the use of NPT, it has been mainly used in reporting the implementation of complex health care intervention prior to the development of a randomized control trial to test their effectiveness.

NPT is a general, generalizable, middle-range theory of implementation that seeks to explain the process of implementation, embedding, and integration of material practices in formally, defined context (May, 2009). It identifies, characterizes and explains mechanism that have been empirically demonstrated to motivate and shape implementation process and affect their outcomes (May et al 2018).

NPT has been developed to identify, characterize and explain empirically identifiable mechanism that motivate and shape implementation process (May et al. 2009), offering a valuable set of conceptual tools to aid understanding of implementation as a dynamic process, effectively assist in the explanation of the success or failure of specific implementation projects (May et al., 2018).

Consequently, NPT provides a means of appraising factors that might promote and inhibit the routine incorporation of complex intervention in everyday life, focusing on the work that people need to ensure interventions become normalized . (Brooks et al; May 2018)

NPT comprises 4 main concepts and identifying these concepts at work during implementation will help to understand the process itself (May and Finch 2009). These components are considered to be dynamic and

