Evaluating a Clinical Ethics Committee (CEC) implementation process in an Oncologic Research Hospital. A process evaluation study using Normalization Process Theory .

interact within the wider context of the intervention, such as existing organizational structures and procedures [May 2018].

Table 1. NPT's 4 core concepts

concept	Key attribute	Working definition
Coherence	Sense-making	The extent to which individuals really understand all the elements of the intervention and the reasons for adopting it a new intervention
Cognitive participation	engagement	The extent to which individuals believe in the innovation provided by the intervention and start to prepare for it
Collective action	enacting	What happens when the intervention is operationalized
Reflexive monitoring	Appraisal	The act of keeping an innovation under review and adapting it intelligently to changing circumstances

NPT will be used as methodological framework to perform PE of the CEC implemented at the Local Health Authority of Reggio Emilia.

3. The evaluation study

PE of complex interventions usually requires a combination of basic quantitative measures of implementation with in-depth qualitative data to provide detailed understandings of intervention functioning on a small scale [Moore 2014].

Our referral framework is the mixed methods approach which, by integrating the quantitative findings with the qualitative findings, aims to provide a more comprehensive picture of the intervention than either method can do [Craig 2008].

I) Quantitative evaluation will include of CEC's activities performed within 16 months since its implementation and survey among all the HPs employed at the Local Health Authority of Reggio Emilia to understand the spread, use and knowledge of the service. These will be used to examine aspects of 'dose' (the quantity of intervention implemented); and the 'reach' of interventions (whether the intended audience comes into contact with the intervention, and how) (Moore 2015).

II) Qualitative methods (semi-structured interview and cognitive survey) will be used to investigate mechanisms of impact and contextual factors among several groups of stakeholders, differently involved in designing, promoting, delivering, and benefitting the intervention. We will use Normalization Process Theory to determine if, and in what ways, the CEC can be successfully 'normalized' (embedded) into clinical practice [Murray 2010, May 2018].

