This is the first study to explore how an ethical case intervention, the CEC, is implemented in practice and the first to use a rigorous approach as NPT to do this. A range of methods of data collection enabling triangulation of data sources and analysis, will be used. Large sample of participants from all the HPs working at the Health Care Authority of Reggio Emilia, and all staff types and grades who were involved in designing, commissioning and delivering the intervention will participate. NPT will inform the interview and survey schedule questions.

Evaluating a Clinical Ethics Committee (CEC) implementation process in an Oncologic Research Hospital. A process evaluation study using Normalization Process Theory .

It will be used also as a framework for data analysis.

Further, we will use data to identify required modifications and to develop practical strategies for enabling and sustaining the CEC delivery in clinical settings.

QUANTITATIVE EVALUATION

The quantitative evaluation aims to assess the implementation process of the CEC by evaluating:

- spread, use, knowledge of the CEC among HPs employed at the Local Health Authority of Reggio Emilia by an anonymous online survey;
- the amount of activities performed by CEC in 16 months and the resources required by the CEC by internal database

Population

For the quantitative evaluation, we chose to focus our study population on all the HPs employed at the Local Health Authority of Reggio Emilia, as CEC is a cross- institution body, dedicated to all the HPs within the health care facility.

Participant eligibility

HPs will be included if they are employed at the Health Care Authority of Reggio Emilia

Recruitment Procedure

The survey will be disseminated among HPs employed at the Local Health Authority of Reggio Emilia. The email will containing all the information related to the study's objectives and a link to the online survey. The email will specify that any personal data will be required to fulfill the survey, which will be anonymous.

Data collection

1) Anonymous survey

We will design, pilot and disseminate an online anonymous survey to assess the spread, use, knowledge of the CEC among HPs employed at the Local Health Authority of Reggio Emilia. The survey will be developed with Google Form with multiple options and closed-ended questions. The surveys' results will be collected in the related Microsoft Excel. The survey will regard HPs' consideration on:

- knowledge

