- spread within health care facility
- access to CEC
- reception of activities provided by the CEC (training, EC, policy guidelines)
- interest to the service

Evaluating a Clinical Ethics Committee (CEC) implementation process in an Oncologic Research Hospital. A process evaluation study using Normalization Process Theory .

-eventual impact of activities developed by CEC on clinical practice(especially regard policy guideline).

2) Internal database

A Microsoft Excel dataset will be created to collect data relating to the activities carried out by the CEC from October 2020 to February 2022. The data will be collected from the internal database of the CEC's Secretariate and by IT application, provided by the Health Care Company, and used by the CEC to save and share the activities carried out.

The following aspects will be analyzed for each of the activities carried out:

CEC's activities	outcomes
CEC's meetings	number of meetings carried out; the presence of CEC's components, duration, topics discussed
Ethics consultation (EC):	number of EC provided, who required the EC, topic of the EC, process and modalities of EC, date of the 'CEC's response, time spent to prepare 'CEC's response
Ethics Training course	hour spent in ethics education; number of participants to the course and their characteristics; procedure/type of education provided; questions/comments by participants
Policy-guidelines published	number of policy guideline published; topic; hours spent to publish the document
Resource employed	time spent related to 'CEC's written report preparation; back-office activities.

It is specified that any sensitive data will be anonymized.

Data analysis

The quantitative data collected by the dataset will be represented using descriptive techniques; that is, they will be summarized in terms of frequency and percentages for categorical variables, mean and standard deviation for symmetric quantitative variables and median and IQR for the remaining ones.

Descriptive statistics will be calculated for general variables. Specifically, continuous variables will be summarized by their mean and SD, or median and interquartile range; categorical variables will be summarized as numbers and percentages.

QUALITATIVE EVALUATION

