The opinions/perspectives on the process implementation of the CEC from users and providers health professionals in terms of barriers/facilitators, expectations and needs will be assessed by using qualitative methods with large samples of participants from all staffs types and grades who were involved in designing, promoting, delivering and benefitting the CEC. Specifically, we will:

- a) interview Managers/Heads who formally supported and promoted the intervention
- b) interview CEC's members who delivered the intervention

Evaluating a Clinical Ethics Committee (CEC) implementation process in an Oncologic Research Hospital. A process evaluation study using Normalization Process Theory .

- c) interview HPs who benefitted the intervention by ethics consultation
- d) perform a cognitive anonymous survey targeting all the HPs who benefitted the intervention by attending the training course promoted by the CEC

Population

The qualitative evaluation is targeting to HPs (physicians, therapists, nurses, social workers) employed by the Local Health Authority of Reggio Emilia, and specifically to:

- Local Managers/Heads of Departments who have been contacted during the dissemination process
- CEC's member
- HPs who submitted an ethics consultation request,
- HPs who attended the training on ethics consultation provided by CEC;

Participant eligibility

Participants will be included if they:

- are working as a Head of Departments / local Manager at the Local health company of Reggio Emilia, who have been contacted by the CEC's president during the dissemination process
- have been a member of the CEC in the last 16 months;
- submitted at least 1 ethics consultation request;
- participated to at least 1 of 5 training courses on ethics consultation promoted by the CEC
- are HPs actually employed at the local Health Authority of Reggio Emilia
- Gave written consent

Recruitment Procedure (Interviews)

The center PI will contact by telephone or e-mail eligible participants, explaining the aims and procedures of the study and providing them with a document containing all the information related to the study's involvement (Attached 1). Participants expressing their interest in participation will be then contacted by telephone by the interviewer/facilitator who, after obtaining written informed consent to participate to the study (Attached 2) and to personal data treatment (Attached 3), will schedule an appointment for the interview.

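### Does the October 2020 to February 2022 activity window contradict the 16 months since implementation in the primary aim?

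*Combined protocol and SAP*

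**What the plan says.** Section 2.1 sets the time point: "This study aims to evaluate the process of a CEC development after 16 months from its implementation". In section 3, under The evaluation study, part I plans a quantitative account of "CEC's activities performed within 16 months since its implementation", meant to inform dose and reach. The opening of the Quantitative evaluation repeats the length: "the amount of activities performed by CEC in 16 months and the resources required by the CEC by internal database". The calendar window appears only under 2) Internal database, as "activities carried out by the CEC from October 2020 to February 2022", with a month but no day at either end.

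Section 3 gives two formal dates. Under Italian Context: "On July, 13, 2020, the Clinical Ethics Committee (CEC) was deliberated by the General Directorate". Under Description of the intervention: "Composition and Regulations were also deliberated by the General Directorate on November 11, 2020". Neither is called the implementation date, and October 2020 is not explained. On procedure, section 3 says "CEC meets once a month through online meetings".

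For the interviews, the eligibility list in the Qualitative evaluation includes people who "have been a member of the CEC in the last 16 months". No reference date is attached.

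**The concern.** Someone who filters a database by month from October 2020 through February 2022 gets 17 calendar months, while the text says 16 throughout. The start also precedes approval of the composition and regulations, so some activity could fall before the membership list and working rules were formally in place. Counting 16 months from either formal date does not give the stated window.

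The study is descriptive, so the activity counts are themselves the quantitative result for dose. Seventeen months of activity described as 16 would overstate any monthly rate worked out from the report. With meetings meant to be monthly, one extra month is one extra expected meeting.

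The membership criterion raises a related worry. If the last 16 months are counted back from each interview, the period moves with the interview date. Someone who served at the start and then left could become ineligible, and such a person may know most about early barriers.

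**Working it through.** **Inputs.** Window: October 2020 to February 2022 (Internal database). Stated length: 16 months (section 2.1; The evaluation study, part I; opening of the Quantitative evaluation). Formal dates: 13 July 2020 and 11 November 2020 (section 3). Study duration: 10 months from ethics approval (end of section 5.3.3). One month is taken as 30.4375 days.

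**Step 1: the plan's own figure.** Elapsed months = 12 × (2022 − 2020) + (2 − 10) = 24 − 8 = 16. The stated figure is reproduced.

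**Step 2: the competing count.** Inclusive calendar months = 16 + 1 = 17. This holds only if both October 2020 and February 2022 are covered in full.

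**Step 3: the range the wording allows.**

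| First day | Last day | Elapsed months |
|---|---|---|
| 31 Oct 2020 | 1 Feb 2022 | 15.05 |
| 15 Oct 2020 | 15 Feb 2022 | 16.03 |
| 1 Oct 2020 | 1 Feb 2022 | 16.03 |
| 1 Oct 2020 | 28 Feb 2022 | 16.92 |

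Sixteen lies near the middle of the range. The mid-month pair shows that 16 does not require February 2022 to be left out.

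**Step 4: the formal dates.** 13 July 2020 + 16 months = 13 November 2021. 11 November 2020 + 16 months = 11 March 2022. Neither yields the stated window. That shows the implementation date is unstated; it does not show that October is wrong. The window opens after the committee was set up and before its rules were approved. The lead before approval is 11 days if the window opens on 31 October, and 31 + 10 = 41 days if it opens on 1 October. The longer lead is 41/516 = 7.9% of the 516 days from 1 October 2020 to 28 February 2022.

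**Step 5: the size of any distortion.** Seventeen months of activity divided by 16 gives 17/16 = 1.0625, or 6.3% too high. Sixteen monthly meetings set against 17 expected give 16/17 = 94%. The two figures need opposite premises: the first assumes activity in all 17 months, the second in only 16. In the second case, dividing by the protocol's own 16 gives 16/16 = 100%.

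**Step 6: whether the plan does either division.** It does not. The Internal database table lists numbers of meetings, consultations and guidelines, attendance, durations, hours and topics. Data analysis summarises them by frequency and percentage, mean and SD, or median and IQR. No rate per month, ratio of held to expected meetings, or benchmark is named. Attendance can be summarised per meeting, so the length of the window need not enter it.

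**Step 7: whether another window is cleaner.** 1 November 2020 to 28 February 2022 is 16 inclusive calendar months, but it still opens ten days before the 11 November approval. Starting on 11 November makes 16 months run to 11 March 2022, past the end of the stated window. Each choice exchanges one mismatch for another.

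**Step 8: the membership criterion.** If the last interviews took place 10 months after February 2022 (an assumed worst case: the 10 months cover the whole study and the approval date is not given), a 16-month look-back would reach only the last 16 − 10 = 6 months of the evaluation period. Even then, it would exclude only people who had already left. The documents report no departure and describe a stable core of 15 members. The topic guides for managers and for members in Appendix 1 speak of these 16 months as the period under evaluation, which supports reading the criterion as that fixed period.

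**The case for a change.** The strongest case for a change is that subtraction shows 16 to be possible but does not tell the extractor which days to include. Counts of events depend on what is included at the ends. In a purely descriptive study the counts are the result, and readers will naturally turn them into monthly figures even though the plan does not. Dating implementation and giving two exact days would cost a few words, and tying membership to the same period would cost a few more.

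Part of this stands. The implementation date is undefined, October 2020 matches neither formal date, the end days are missing, and the membership period has no anchor. But the records come from the secretariat's own database, and the table asks for the date of each consultation response. An analyst can therefore see what falls at the edges and report counts with the months already named. A reader given those months can form any rate without relying on the word 16.

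The objection that October precedes approval of the rules is weaker. The aim is to evaluate how the committee developed, so start-up work by a body that already existed is within scope.

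**Conclusion.** No change is needed. The window agrees with 16 months by ordinary date difference and differs only under a full inclusive count of 17, an ambiguity of up to one month or about 6%. It bears on how the period is described. It does not bear on any planned estimate, test, threshold or sample size, because the plan contains none that uses the length of the period. Following the text as written gives sound descriptive counts over a named span.

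This conclusion rests on three readings: that implementation is not tied to the 11 November approval, which no section says; that results are reported with their calendar dates; and that the membership criterion refers to the evaluation period, as the topic guides suggest. If the report were to add monthly rates or a ratio of held to expected meetings, the exact first and last days would need to be stated beside them. Analysts would ordinarily do that, and it needs no amendment now.
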